# 7 STATISTICAL ANALYSES OF THE EFFICACY ENDPOINTS

The analyses of the primary and secondary endpoints will be carried out of both the ITT and PP populations. Moreover, as for the Step Test and the Quality of Life (i.e. EQ-5D), a further analysis in the subpopulation of the "Continuous Quitter" will be presented.

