## 7.1 Analysis of primary endpoint

The primary endpoint aims to compare the efficacy of HnB and EC in terms of quit rates at week 12 by means a non-inferiority threshold of 15%.

A "Continuous Quitter" is defined as a subject who has a number of conventional cigarette/day equal to zero from Visit 4 to Visit 6. The Farrington-Manning Score Test for Proportion Difference will be used for comparing the quit rates of the two groups. The SAS® PROC FREQ with the METHOD=FM option will be used. The quit rates of the two groups, along with the relevant 95% Confidence Intervals, will be summarized in Table E.1 (Appendix 2).

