### 7.5 Step test by visit

The Step test data will be presented as descriptive summary table by visit. The seven items regarding Heart Rate and Oxygen Saturation (i.e. Baseline, Step 1 to 5 and Baseline condition recovery time) will be analysed by HR and SpO2. The two items, (i.e. Stop time and VO2MAX, will be analysed using the same methods (Table E.7a). In details, the latter, is the result of the so called “Chester Step Test” who was computed for each subject at site and reported in the eCRF.

An inferential analysis will be carried out on the changes from baseline by item. The results will be presented in Table E.7b. The data will also be listed (Appendix 3: Listing D.8). The analysis will be presented by all subjects and “Continuous Quitters”.

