## 8 STATISTICAL ANALYSES OF SAFETY ENDPOINTS

The Safety will be evaluated on all the subjects in the study through the analysis of the Adverse Events (AEs), i.e. those events, occurred during the study, which could be related or not related with the devices, and the Vital Signs.

No methods for replacing missing values will be applied. The Safety population will be considered for this analysis, therefore all the listings will be built with reference to the full set of enrolled patients. As for the Vital Signs, a further analysis in the subpopulation of the “Continuous Quitter” will be presented.

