## EFFICACY ENDPOINTS

	e-CIG VS. IQOS Statistical Analysis Plan Version 2.0	Doc code: BIOSTAT.SAP.02
		Pag. 42 of 115

Sponsor: Center for Tobacco Research, Cessation and Prevention, [name]  
Protocol: Progetto e-cig vs IQOS

Table E.1a Summary of the Primary End-point. Quit Rate at all visits  
Population: <Per-Protocol/Intention-To-Treat>

			Group HnB N=XXXX	Group EC N=XXXX
Quit rate	Visit 1	N(%)	XXX (XX.X%)	XXX (XX.X%)
	Visit 2	N(%)	XXX (XX.X%)	XXX (XX.X%)
	...	N(%)	XXX (XX.X%)	XXX (XX.X%)
	Visit n	N(%)	XXX (XX.X%)	XXX (XX.X%)

<File: [..]\Work\_In\_Progress\[..]\Statistica\Programmi\xxxxx.sas>

<Source: [..]\Work\_In\_Progress\[..]\Gestione Dati\Dati SAS\xxxxx.sas7bdat>      Generated on XXXXXXXXXX XX:XX

As for the PP population, a "Continuous Quitter" is defined as the subject who did not smoke conventional cigarettes from visit 4 to visit 6

The p-value was derived from the XXXX test

For further information see Listing X.X

Sponsor: Center for Tobacco Research, Cessation and Prevention, [name]  
Protocol: Progetto e-cig vs IQOS

Table E.1b Summary of the Primary End-point. Quit Rate at final visit comparison  
Population: <Per-Protocol/Intention-To-Treat>

		Group HnB N=XXXX	Group EC N=XXXX
Quit Rate	Rate 95%CI	XX.X% [XX.XX,XXX.X]	XX.X% [XX.XX,XXX.X]

H0: P1-P2 ≤ -Margin  
H1: P1-P2 > -Margin

Margin=X.XXX

Score (Farrington-Manning)

Proportion Difference	ASE (F-M)	Z	Pr>Z
X.XXXX	X.XXXX	X.XXXX	X.XXXX

Noninferiority Limit	95% Confedent Limits	
X.XXXX	X.XXXX	X.XXXX

<File: [..]\Work\_In\_Progress\[..]\Statistica\Programmi\xxxxx.sas>

<Source: [..]\Work\_In\_Progress\[..]\Gestione Dati\Dati SAS\xxxxx.sas7bdat>      Generated on XXXXXXXXXX XX:XX

As for the PP population, a "Continuous Quitter" is defined as the subject who did not smoke conventional cigarettes from visit 4 to visit 6  
For further information see Listing X.X

	e-CIG VS. IQOS Statistical Analysis Plan Version 2.0	Doc code: BIOSTAT.SAP.02
		Pag. 44 of 115

Sponsor: Center for Tobacco Research, Cessation and Prevention, [name]  
Protocol: Progetto e-cig vs IQOS

Table E.2a Summary of Smoking Reduction derived from the use of HnB and EC at week 12  
Population: <Per-Protocol/Intention-To-Treat>

		Group HnB	Group EC	p-value
		N=XXXX	N=XXXX	
Smoking Reduction	Rate 95%CI	XX.X% [XX.XX,XXX.X]	XX.X% [XX.XX,XXX.X]	X.XXXX

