Table E.5 Summary of the Biomarkers of Biological Exposure (BoBE) - eCO (ppm)  
Population: <Per-Protocol/Intention-To-Treat>

	Visit	Observed Values at Visit						Changes From Visit 1 to Visits n							
		N	N miss	Mean	STD	CI 95%	Median	Range (Q1-Q3)	N	N miss	Mean	STD	CI 95%	Median	Range (Q1-Q3)
Group HnB	Screening	XX	XX	XX.XX	XX.XX	[XX.XX,XXX.X]	XX.XX	(XX.XX - XXX.X)							
	Visit 1	XX	XX	XX.XX	XX.XX	[XX.XX,XXX.X]	XX.XX	(XX.XX - XXX.X)							
	Visit 2	XX	XX	XX.XX	XX.XX	[XX.XX,XXX.X]	XX.XX	(XX.XX - XXX.X)							
	Visit 3	XX	XX	XX.XX	XX.XX	[XX.XX,XXX.X]	XX.XX	(XX.XX - XXX.X)							
	Visit 4	XX	XX	XX.XX	XX.XX	[XX.XX,XXX.X]	XX.XX	(XX.XX - XXX.X)							
	Visit 5	XX	XX	XX.XX	XX.XX	[XX.XX,XXX.X]	XX.XX	(XX.XX - XXX.X)							
	Visit 6	XX	XX	XX.XX	XX.XX	[XX.XX,XXX.X]	XX.XX	(XX.XX - XXX.X)							
	Follow-up	XX	XX	XX.XX	XX.XX	[XX.XX,XXX.X]	XX.XX	(XX.XX - XXX.X)	XX	XX	XX.XX	XX.XX	[XX.XX,XXX.X]	XX.XX	(XX.XX - XXX.X)
Group EC	Screening	XX	XX	XX.XX	XX.XX	[XX.XX,XXX.X]	XX.XX	(XX.XX - XXX.X)							
	Visit 1	XX	XX	XX.XX	XX.XX	[XX.XX,XXX.X]	XX.XX	(XX.XX - XXX.X)							
	Visit 2	XX	XX	XX.XX	XX.XX	[XX.XX,XXX.X]	XX.XX	(XX.XX - XXX.X)							
	Visit 3	XX	XX	XX.XX	XX.XX	[XX.XX,XXX.X]	XX.XX	(XX.XX - XXX.X)							
	Visit 4	XX	XX	XX.XX	XX.XX	[XX.XX,XXX.X]	XX.XX	(XX.XX - XXX.X)							
	Visit 5	XX	XX	XX.XX	XX.XX	[XX.XX,XXX.X]	XX.XX	(XX.XX - XXX.X)							
	Visit 6	XX	XX	XX.XX	XX.XX	[XX.XX,XXX.X]	XX.XX	(XX.XX - XXX.X)							
	Follow-up	XX	XX	XX.XX	XX.XX	[XX.XX,XXX.X]	XX.XX	(XX.XX - XXX.X)	XX	XX	XX.XX	XX.XX	[XX.XX,XXX.X]	XX.XX	(XX.XX - XXX.X)

p-value=X.XXXX

e-CIG VS. IQOS  
Statistical Analysis Plan  
Version 2.0

Doc code:  
BIOSTAT.SAP.02

Pag. 59 of 115

Sponsor: Center for Tobacco Research, Cessation and Prevention, [name]  
Protocol: Progetto e-cig vs IQOS

Table E.6 Summary of EQ-5D Questionnaire (scores). < Group HnB / Group EC >  
Population: <Per-Protocol/Intention-To-Treat/Continuous Quitters>

Parameter	Visit	Observed Values at Visit							Changes From Visit 1 to Visits n						
		N	N miss	Mean	STD	CI 95%	Median	min-max	N	N miss	Mean	STD	CI 95%	Median	min-max
Mobility (1-5)	Visit 1	XX	XX	XX.X	XX.X	[X.X , X.X]	XX.X	(X - X)							
	Visit 4	XX	XX	XX.X	XX.X	[X.X , X.X]	XX.X	(X - X)							
	Visit 5	XX	XX	XX.X	XX.X	[X.X , X.X]	XX.X	(X - X)							
	Visit 6	XX	XX	XX.X	XX.X	[X.X , X.X]	XX.X	(X - X)							
	Visit 7	XX	XX	XX.X	XX.X	[X.X , X.X]	XX.X	(X - X)	XX	XX	XX.X	XX.X	[X.X , X.X]	XX.X	(X - X)

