Self-care (1-5)	Visit 1	XX	XX	XX.X	XX.X	[X.X , X.X]	XX.X	(X - X)							
	Visit 4	XX	XX	XX.X	XX.X	[X.X , X.X]	XX.X	(X - X)							
	Visit 5	XX	XX	XX.X	XX.X	[X.X , X.X]	XX.X	(X - X)							
	Visit 6	XX	XX	XX.X	XX.X	[X.X , X.X]	XX.X	(X - X)							
	Visit 7	XX	XX	XX.X	XX.X	[X.X , X.X]	XX.X	(X - X)	XX	XX	XX.X	XX.X	[X.X , X.X]	XX.X	(X - X)
.....															
Health-today (0-100)	Visit 1	XX	XX	XX.X	XX.X	[X.X , X.X]	XX.X	(X - X)							
	Visit 4	XX	XX	XX.X	XX.X	[X.X , X.X]	XX.X	(X - X)							
	Visit 5	XX	XX	XX.X	XX.X	[X.X , X.X]	XX.X	(X - X)							
	Visit 6	XX	XX	XX.X	XX.X	[X.X , X.X]	XX.X	(X - X)							
	Visit 7	XX	XX	XX.X	XX.X	[X.X , X.X]	XX.X	(X - X)	XX	XX	XX.X	XX.X	[X.X , X.X]	XX.X	(X - X)

<File: [..]\Work\_In\_Progress\[..\]Statistica\Programmi\xxxxx.sas>

<Source: [..]\Work\_In\_Progress\[..\]Gestione Dati\Dati SAS\xxxxx.sas7bdat>

Generated on XXXXXXXX XX:XX

For further information see Listing X.X

e-CIG VS. IQOS  
Statistical Analysis Plan  
Version 2.0

Doc code:  
BIOSTAT.SAP.02

Pag. 60 of 115

Sponsor: Center for Tobacco Research, Cessation and Prevention, [name]  
Protocol: Progetto e-cig vs IQOS

Table E.7a Summary of Step Test by group < Group HnB / Group EC >  
Population: <Per-Protocol/Intention-To-Treat>

Parameter	Visit	Observed Values at Visit						Changes From Visit 1 to Visit 7							
		N	N miss	Mean	STD	CI 95%	Median	Range (Q1-Q3)	N	N miss	Mean	STD	CI 95%	Median	Range (Q1-Q3)
Baseline HR	Visit 1	XX	XX	XX.XX	XX.XX	[XX.XX,XXX.X]	XX.XX	(XX.XX - XXX.X)							
	Visit 4	XX	XX	XX.XX	XX.XX	[XX.XX,XXX.X]	XX.XX	(XX.XX - XXX.X)							
	Visit 6	XX	XX	XX.XX	XX.XX	[XX.XX,XXX.X]	XX.XX	(XX.XX - XXX.X)							
	Visit 7	XX	XX	XX.XX	XX.XX	[XX.XX,XXX.X]	XX.XX	(XX.XX - XXX.X)	XX	XX	XX.XX	XX.XX	[XX.XX,XXX.X]	XX.XX	(XX.XX - XXX.X)
SpO2	Visit 1	XX	XX	XX.XX	XX.XX	[XX.XX,XXX.X]	XX.XX	(XX.XX - XXX.X)							
	Visit 4	XX	XX	XX.XX	XX.XX	[XX.XX,XXX.X]	XX.XX	(XX.XX - XXX.X)							
	Visit 6	XX	XX	XX.XX	XX.XX	[XX.XX,XXX.X]	XX.XX	(XX.XX - XXX.X)							
	Visit 7	XX	XX	XX.XX	XX.XX	[XX.XX,XXX.X]	XX.XX	(XX.XX - XXX.X)	XX	XX	XX.XX	XX.XX	[XX.XX,XXX.X]	XX.XX	(XX.XX - XXX.X)
Step 1 HR	Visit 1	XX	XX	XX.XX	XX.XX	[XX.XX,XXX.X]	XX.XX	(XX.XX - XXX.X)							
	Visit 4	XX	XX	XX.XX	XX.XX	[XX.XX,XXX.X]	XX.XX	(XX.XX - XXX.X)							
	Visit 6	XX	XX	XX.XX	XX.XX	[XX.XX,XXX.X]	XX.XX	(XX.XX - XXX.X)							
	Visit 7	XX	XX	XX.XX	XX.XX	[XX.XX,XXX.X]	XX.XX	(XX.XX - XXX.X)	XX	XX	XX.XX	XX.XX	[XX.XX,XXX.X]	XX.XX	(XX.XX - XXX.X)

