## SAFETY ENDPOINTS

	e-CIG VS. IQOS Statistical Analysis Plan Version 2.0	Doc code: BIOSTAT.SAP.02
		Pag. 63 of 115

Sponsor: Center for Tobacco Research, Cessation and Prevention, [name]  
Protocol: Progetto e-cig vs IQOS

Table S.1 Summary of Extent of Exposure by group  
Population: Safety

		Group HnB	Group EC
		N=XXX	N=XXX
Extent of Exposure	N	XX	XX
	N missing	XX	XX
	Mean	XX.X	XX.X
	Std. deviation	XX.X	XX.X
	Median	XX.X	XX.X
	Q1-Q3	XX.X - XX.X	XX.X - XX.X

---

<File: [..]\Work\_In\_Progress\[..]\Statistica\Programmi\xxxxx.sas>  
<Source: [..]\Work\_In\_Progress\[..]\Gestione Dati\Dati SAS\xxxxx.sas7bdat>      Generated on XXXXXXXXXX XX:XX  
The Extent of exposure is computed as (Visit 6 date - Baseline date)  
For further information see Listing X.X

	e-CIG VS. IQOS Statistical Analysis Plan Version 2.0	Doc code: BIOSTAT.SAP.02
		Pag. 64 of 115

Sponsor: Center for Tobacco Research, Cessation and Prevention, [name]  
Protocol: Progetto e-cig vs IQOS

Table S.2 Summary of Adverse Drug Reactions by group  
Population: Safety

	Group HnB N=XXX	Group EC N=XXX
ADRs	XX (XX.X%)	XX (XX.X%)
SADRs	XX (XX.X%)	XX (XX.X%)
Related ADRs	XX (XX.X%)	XX (XX.X%)

<File: [..]\Work\_In\_Progress\[..]\Statistica\Programmi\xxxxx.sas>  
<Source: [..]\Work\_In\_Progress\[..]\Gestione Dati\Dati SAS\xxxxx.sas7bdat>

Generated on XXXXXXXXXX XX:XX

The percentages are calculated on the total of the enrolled patients by group  
ADRS classified as Possible/Probably/Definite are considered as Related ADRS  
For further information see Listing X.X

e-CIG VS. IQOS  
Statistical Analysis Plan  
Version 2.0

Doc code:  
BIOSTAT.SAP.02

Pag. 65 of 115

Sponsor: Center for Tobacco Research, Cessation and Prevention, [name]  
Protocol: Progetto e-cig vs IQOS

Table S.3 Summary of Vital Signs by group < Group HnB / Group EC >  
Population: <Safety/Continuous Quitters>

Parameter <Unit>	Visit	Observed Values at Visit							Changes From Visit 1 to Visits 6 and 7						
		N	N miss	Mean	STD	CI 95%	Median	Range (Q1-Q3)	N	N miss	Mean	STD	CI 95%	Median	Range (Q1-Q3)
parameter #1 <um>	Baseline	XX	XX	XX.XX	XX.XX	[XX.XX,XXX.X]	XX.XX	(XX.XX - XXX.X)							
	Visit 2	XX	XX	XX.XX	XX.XX	[XX.XX,XXX.X]	XX.XX	(XX.XX - XXX.X)							
	. . . . . Follow-up	XX	XX	XX.XX	XX.XX	[XX.XX,XXX.X]	XX.XX	(XX.XX - XXX.X)	XX	XX	XX.XX	XX.XX	[XX.XX,XXX.X]	XX.XX	(XX.XX - XXX.X)

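### The Continuous Quitter flag closes at Visit 6 but also selects the population for week-24 results, so people who resume smoking after week 12 would be summarised at Visit 7 as continuous quitters

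*SAP*

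**What the plan says.** **Definition.** SAP 7.1 says that a Continuous Quitter "is defined as a subject who has a number of conventional cigarette/day equal to zero from Visit 4 to Visit 6". The footnotes to mock Tables E.1a and E.1b repeat the window for the PP population: the term "is defined as the subject who did not smoke conventional cigarettes from visit 4 to visit 6". No version extends to Visit 7, and the SAP definition does not mention eCO.

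**Use as a subpopulation.** The introduction to SAP Section 7 plans, "as for the Step Test and the Quality of Life (i.e. EQ-5D), a further analysis in the subpopulation of the" Continuous Quitters. SAP 7.4 and 7.5 repeat this; 7.5 reads "The analysis will be presented by all subjects and" Continuous Quitters. The introduction to Section 8 adds: "As for the Vital Signs, a further analysis in the subpopulation of the" Continuous Quitters.

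**Visits reported.**
- Table E.6 (EQ-5D) is headed "Population: <Per-Protocol/Intention-To-Treat/Continuous Quitters>" and runs from Visit 1 to Visit 7. Its change cells are filled only on the Visit 7 row.
- Table S.3 (vital signs) lists Continuous Quitters and has a column "Changes From Visit 1 to Visits 6 and 7".
- Table E.7a (step test) has a column "Changes From Visit 1 to Visit 7". Its population line names only PP and ITT, so the Continuous Quitter version rests on the text of 7.5.

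**Status at Visit 7.** The protocol visit schedule and SAP Appendix 4 both mark self-reported smoking and eCO at Visit 7. The Efficacy assessment section of the protocol defines abstinence as no smoking since the previous visit with eCO of 10 ppm or less, to be derived at each visit, week 24 included.

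**The concern.** A reader of the week-24 rows will take Continuous Quitters to be people who are still not smoking. Under the definition as written, they are people who were not smoking between weeks 4 and 12. Free product supply ends at Visit 6, and 12 weeks pass before Visit 7, so some resumption of smoking is possible and the label would hide it.

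The subgroup is of interest because it shows how quality of life, exercise capacity and vital signs change in people who stop smoking. If current smokers are mixed into the week-24 summary and their values move back towards baseline, the change looks smaller than it is in those who stayed abstinent. If relapse differs between HnB and EC, the dilution differs too, and part of any contrast between arms at week 24 would reflect relapse rather than the effect of stopping.

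**Working it through.** **Plan's own figure.** The only related figure is the sample size, which this point leaves unchanged. With reference rate 0.25, margin 0.15, one-sided alpha 0.05 and power 0.80, the Farrington-Manning null proportions are 0.1891 and 0.3391:

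n = [(1.645 × √(0.1891 × 0.8109 + 0.3391 × 0.6609) + 0.842 × √(2 × 0.25 × 0.75)) / 0.15]² ≈ 103.5, rounded up to 104 per group, as stated.

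**Flag and reported visits, side by side.**

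| Analysis | Source of the subgroup | Flag window | Change reported to |
|---|---|---|---|
| EQ-5D | 7, 7.4, Table E.6 | Visits 4–6 | all later visits (7.4 text); Visit 7 row filled in the shell |
| Step test | 7, 7.5 text | Visits 4–6 | Visit 7 (E.7a column heading) |
| Vital signs | Section 8 introduction, Table S.3 | Visits 4–6 | Visits 6 and 7 |

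**Worked record.** A participant with 0, 0, 0 and 15 cigarettes/day at Visits 4, 5, 6 and 7 meets the definition and enters the Visit 7 summary as a Continuous Quitter. The Per-Protocol V7 population does not prevent this, because SAP Section 4 and the DRM minute require completion of Visit 7, not abstinence at it. Its fall from 193 to 177 (16 subjects) says nothing about who was smoking.

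**Size of the group (rough guide).** The protocol's planning quit rate of 20–25% in 110 per arm gives 0.20 × 110 = 22 to 0.25 × 110 = 27.5 per arm. The flag's longer window makes the group smaller than this; the absence of an eCO condition works the other way.

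**Dilution.** Let r be the share of the flagged group smoking again by week 24, and k the share of the change that relapsers keep. Neither is in the documents. Assume r from 10% to 50% and k of 0 or 0.5. Assume also that relapsers would otherwise have changed as much as the others and attend Visit 7 equally often.

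Observed change ÷ change in sustained quitters = 1 − r(1 − k)

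| r | k = 0 | k = 0.5 |
|---|---|---|
| 10% | 0.90 | 0.95 |
| 30% | 0.70 | 0.85 |
| 50% | 0.50 | 0.75 |

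In numbers of people, 0.10 × 22 = 2.2 to 0.50 × 27.5 = 13.75, so about 2 to 14 per arm would carry the label at week 24 while smoking.

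**Unequal relapse.** If relapse were 20% in one arm and 40% in the other, with k = 0 and the same true change in both, the arms would differ by 0.80 − 0.60 = 0.20 of the full change with no real difference in the effect of stopping.

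**The case against.** The strongest reply is that a cohort fixed at the primary timepoint and followed to week 24 is a legitimate descriptive analysis, and that the SAP never says the subgroup must represent people abstinent at week 24. That stands. The defect is then the label and the missing companion group, since neither Table E.6 nor Table S.3 says that membership was fixed at week 12. Such a cohort should be kept, not replaced.

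A reader might infer from Table E.6 that the Visit 7 change is the only EQ-5D change to be reported. The documents do not support this. SAP 7.4 promises changes to all subsequent visits, and the heading of the change columns in E.6 is generic. Filling only the last row is a habit of these templates: Table E.5 does it, and so does Table E.4a1 for a questionnaire with no baseline assessment. Only E.7a names Visit 7 alone.

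Nor is it certain that the inferential EQ-5D comparison falls at Visit 7. SAP 7.4 refers to the final visit, and the title of Table E.1b uses that phrase for the quit-rate comparison, whose endpoint is week 12. On that reading the flag and the test match.

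Relapse will also be visible elsewhere: in the quit rates by visit in Table E.1a, the 24-week eCO-checked rate in Table E.2b, and the cigarettes/day and eCO in Listing D.4b. That helps a careful reader, but it does not correct the week-24 summaries themselves.

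**Conclusion.** The point holds as a labelling and subgroup-definition problem confined to Visit 7. The link is clearest for Tables E.6 and S.3, which name the subgroup. For the step test it comes from the text of 7.5. For vital signs the instruction is in the Section 8 introduction; 8.3 does not mention it.

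No size can be computed from the documents. As an illustration, 10% to 50% relapse gives an understatement of 10% to 50% if relapsers keep none of the change, or 5% to 25% if they keep half. It is zero if nobody relapses, and its direction assumes that the change reverses when smoking resumes. It would be tempting to add that relapse peaks in this interval; the protocol says only that free supply stops.

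The week-12 primary endpoint, the sample size and all results at Visits 4 to 6 are untouched. The analysis is secondary and largely descriptive, so this is a cheap improvement worth making and not a threat to the main conclusion.

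**What to change.** 1. In SAP 7.1, relabel the existing group 'abstinent weeks 4–12'. Keep it as a fixed cohort, and footnote in Tables E.6, E.7a and S.3 that membership was set at week 12 and does not imply abstinence at week 24.
2. Add a flag 'Continuous Quitter to week 24': zero cigarettes/day from Visit 4 to Visit 7, with eCO of 10 ppm or less as in the protocol's abstinence definition. Count a missing Visit 7 as not a quitter, in line with the drop-out rule for response endpoints in the DRM minute (2.4). The week-12 definition has no eCO condition, so the footnotes should state both definitions in full.
3. Show the Visit 7 rows and the changes to Visit 7 for the new flag beside the week-12 cohort.
4. Fill the Visit 4 to 6 change rows in Table E.6, as SAP 7.4 already states, and the Visit 4 and Visit 6 change rows in Table E.7a. Add the Continuous Quitter population to the E.7a shell so that it agrees with 7.5.

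The cost is SAP wording, one more derived flag and some extra table rows, all from data already collected. The downside is a smaller week-24 subgroup. Both groups are selected after randomisation, so comparisons between arms within them should be read as descriptive.

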## **Statistical Analysis Plan**

### **Sample size calculation**

We assume that:

- current e-vapor products provide a 25% quitting rate in clinical trials (1,2)
- non-inferiority in quit rates means that the proportion of subjects successfully quitting smoking using the test product is not worse than the proportion of subjects quitting smoking using the alternative or reference product, this difference is allowed a tolerance of 15% (3,4).

For sample size definition, we used the Farrington-Manning Score Test for Proportion Difference, assuming:

- asymptotic normal distribution, upper one-tailed
- alpha 0.05
- nominal power 0.80

Thus:

- Null Proportion Diff. -0.15
- Ref Proportion 0.25
- N per group: 104

Consequently, a total of 220 smokers not intending to quit (110 per each arm) will be recruited.

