### **6.3 Demographics and smoking habits**

The following demographic and baseline variables will be analyzed: age, gender at birth and education (Appendix 2: Table D.2a). As for the smoking habits, a dedicated table, in which details are presented as summary and frequency tables, will be prepared. Number of cigarettes per day will be summarized (Appendix 2: Table D.2b).

These data will also be listed (Appendix 3: Listing D.4, Listing D.5).

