### **6.7 Fagestorm test for nicotine dependence**

	e-CIG VS. IQOS Statistical Analysis Plan Version 2.0	Doc code: BIOSTAT.SAP.02
		Pag. 12 of 115

The results of the Fagestorm test for nicotine dependence (FTCD) will be presented as frequencies and percentages for the single questions and total scores derived from the questionnaire through n, missing, mean, standard deviation and 25th, 50th, 75th percentiles (Appendix 2: Table D.7). These data will also be listed (Appendix 3: Listing D.11).

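### The valid but unadjusted primary quit-rate test could be supplemented by a prespecified risk difference adjusted for V1 cigarettes/day and V1 eCO: an improvement, not an error

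*SAP*

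**What the plan says.** **Primary test.** SAP 7.1 states: "The Farrington-Manning Score Test for Proportion Difference will be used for comparing the quit rates of the two groups". It is run in PROC FREQ with no covariate or stratum, in both the ITT and PP populations (SAP 7). Mock Table E.1b holds crude rates, their difference, a Z statistic, a p-value and confidence limits. Neither document plans an adjusted primary or sensitivity analysis of the quit rate.

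**Protocol.** The sample size section uses FM with "asymptotic normal distribution, upper one-tailed", alpha 0.05, "nominal power 0.80", "Null Proportion Diff. -0.15", "Ref Proportion 0.25" and "N per group: 104". The primary endpoint paragraph under Statistics fixes the 15-point threshold and counts losses to follow-up as failures, but names no test. Randomisation is 1:1 in blocks of 4, with no stratification factor named. The only adjustment planned in the protocol is for the urinary metabolites at week 4.

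**Pre-treatment data.** The visit schedule and its description put cigarettes/day and eCO at V1. Mock Table D.2b also tabulates both at screening. On dependence, SAP 6.7 says "The results of the Fagestorm test for nicotine dependence (FTCD) will be presented as frequencies and percentages", together with a total score. V1 cigarettes/day is also the reference for the reducer endpoint (SAP 7.2.1), and V1 eCO is the baseline for the eCO change analysis (SAP 7.3).

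**The concern.** How heavily someone smokes, and how dependent they are, can be expected to relate to whether they stop. If so, part of the spread in quit status is predictable before randomisation, and a crude comparison leaves that part in the standard error. With no stratification, neither the design nor the analysis takes account of a chance difference between arms in these variables. At stake are the width of the interval set against -15 points, in a trial with a little over 80% power, and a planned answer if the arms happen to differ at baseline.

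**Working it through.** **1. Reproduce the plan's figure.** Inputs from the protocol's sample size section: 25% reference rate, null difference -0.15, one-sided alpha 0.05, power 0.80. A 25% rate in the HnB arm is implied rather than stated.

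- Unpooled formula: n = 2 × 0.25 × 0.75 × (1.645 + 0.842)² / 0.15² = 103.04, so 104 per group.
- FM formula, with null variance from the restricted estimates (0.189 for HnB, 0.339 for EC): power is 0.798 at 103, 0.802 at 104 and 0.821 at 110.

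Both give 104, so sizing and analysis agree.

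**2. Unadjusted precision at 110 per arm.** SE = √(2 × 0.25 × 0.75 / 110) = 0.0584. Power = Φ(0.15/0.0584 − 1.645) = 82.2%.

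**3. Effect of adjustment, by approximation.** If the covariates explain a share R² of the variance in quit status, the variance of the marginal risk difference is multiplied by about (1 − R²). R² is assumed, since the documents give nothing from which to derive it.

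| Assumed R² | SE at 110 | Power at 110 | n per arm for 80% | 110 per arm is worth |
|---|---|---|---|---|
| 0 | 0.0584 | 82.2% | 104 | 110 |
| 0.02 | 0.0578 | 82.9% | 101 | 112 |
| 0.05 | 0.0569 | 83.9% | 98 | 116 |
| 0.10 | 0.0554 | 85.6% | 93 | 122 |
| 0.15 | 0.0538 | 87.3% | 88 | 129 |

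**4. Simulation with three fitted covariates.** The approximation ignores the cost of estimating the coefficients. The setting was 110 per arm, 25% quitting in both arms, 4,000 trials, and a logistic model on arm and three independent covariates, standardised to a risk difference.

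| R² | Adjusted/unadjusted variance | Power unadjusted | Power adjusted |
|---|---|---|---|
| 0 | 1.017 | 82.4% | 82.1% |
| 0.016 | 1.005 | 82.8% | 82.9% |
| 0.039 | 0.978 | 82.0% | 82.7% |
| 0.079 | 0.923 | 81.8% | 84.6% |
| 0.128 | 0.886 | 82.7% | 86.0% |

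A second simulation (3,000 trials, three equal independent covariates) gave variance reductions of 2.8%, 7.3% and 11.8% when the covariates together discriminate quitters with AUC 0.63, 0.69 and 0.74, and about zero or slightly negative at AUC 0.58 or below. A third gave ratios of about 1.02 with no prognostic value, then 0.97, 0.93 and 0.85 as prediction strengthened.

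**5. Convert to power**, if the adjusted analysis leads:

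- Variance down 3%: Φ(0.15/(0.0584 × √0.97) − 1.645) = 83.2%.
- Variance down 15%: Φ(0.15/(0.0584 × √0.85) − 1.645) = 87.3%.
- Variance up 2%: the same formula gives a loss of about 0.7 of a point.

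**6. Error rate at the margin.** With true rates of 10% and 25%, the adjusted delta-method test rejected in about 5.6% to 5.7% of simulated trials, against 5.0% to 5.2% for FM (Monte Carlo SE about 0.4 points).

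**The case against.** The strongest case against is that nothing here needs repair. FM sized the trial and analyses it, and power exceeds the planned 80%. A reader might infer that chance imbalance biases the crude comparison. It does not: under randomisation that variability is already in the test's standard error and error rate. This stands, and it is why the point is an improvement only.

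A reader might also infer that precision is certainly being lost. The documents do not support that. Entry requires at least 10 cigarettes/day and no intention to quit, which narrows the covariate range. The dependence questionnaire itself contains a cigarettes/day item, so the covariates overlap. Weak prediction is plausible and would bring no gain.

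Nor are the variables confined to baseline tables, given the secondary endpoints in SAP 7.2.1 and 7.3. The dependence score cannot simply be taken as pre-treatment: it is in neither visit schedule, and its timing rests on its place in SAP section 6 and the baseline mock tables.

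Timing is a fair objection. SAP 2.0 (8 July 2020) follows the data review meeting of 10 June. The minute records that no change to SAP 1.1 was requested, and that the database would be unfrozen for the last queries and then frozen again. Choosing a new lead analysis at that stage of an open-label trial invites doubt about prespecification.

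Finally, if FM leads, the primary test's power does not change. That is true. What remains is a prespecified supportive estimate, probably narrower, and a planned response to imbalance.

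**Conclusion.** The point holds as a low-cost improvement. SAP 7.1 is valid, consistent with its sizing and adequately powered on its own assumptions. It leaves unused two pre-treatment measurements that could sharpen the same risk difference against the same margin.

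The gain is modest and conditional: roughly 3% to 15% of variance for moderate to strong prediction, and nothing, or a loss of up to about 2%, if the covariates barely predict quitting. The increase in power from about 82% to about 83–87% applies only if the adjusted analysis leads. These figures assume 25% quitting in both arms, 110 per arm, one-sided alpha 0.05 and an assumed prognostic strength.

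The decision level matters too. Table E.1b shows 95% limits, whereas sizing used one-sided 0.05. If a two-sided 95% lower limit decided the question, FM power at 110 per arm would be about 73%, and any gain in precision would count for more.

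**What to change.** Add to SAP 7.1, before outcomes are analysed by arm:

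- **Model.** Logistic regression of week-12 quit status on arm, V1 cigarettes/day and V1 eCO, both continuous. Add the dependence total only if it is confirmed to have been collected before randomisation.
- **Estimate.** Average each participant's predicted risk under HnB and under EC over the whole ITT population and take the difference, with a robust or delta-method interval. This keeps the meaning of the 15-point margin, which a conditional odds ratio would not.
- **Decision level.** Compare the lower limit with -15 points at the alpha used for sizing.
- **Missing data.** Fill a missing baseline covariate simply, for example with the overall mean, so that no one is dropped. Keep loss to follow-up as failure.
- **Order.** State in advance which analysis leads. The safer order is FM as lead and the adjusted estimate as the prespecified supportive analysis. Label it post hoc if outcomes have already been seen by arm.

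The cost is a paragraph, a few lines of SAS, covariates to lock now, two results to report, and a negligible loss of precision in the adjusted estimate if the covariates prove uninformative.
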